Study population	
Inclusion criteria:
 
 1. Patients identified as "Asia type" DEL blood group; 2. Male patients, or female patients ≥ 49 years of age, or female patients with severe illness and no further pregnancy plan; 3. Patients with need for blood transfusion in line with the guidelines for internal or surgical and traumatic blood transfusion: 
 * In line with the guidelines for internal blood transfusion of the Technical Specifications for Clinical Blood Transfusion, red blood cell transfusion is considered for the patients with chronic anemia caused by excessive destruction of red blood cells, loss or production disorders with hypoxic symptoms; hemoglobin $<60\text{g/L}$ or hematocrit <0.2; * In line with the guidelines for surgical and traumatic blood transfusion of the Technical Specifications for Clinical Blood Transfusion, the red blood cell transfusion is considered for the patients who need to increase blood oxygen carrying capacity with normal or corrected blood volume; hemoglobin $<70\text{g/L}$; 4. Signing the informed consent voluntarily for blood transfusion treatment before the trial. Patients and/or their legal representatives have ability to fully understand the trial content, process and possible adverse reactions, and enable patients to comply with the visiting and inspections specified in the protocol. 
Exclusion criteria:
 
 1. Patients who had a transfusion reverse reaction in a previous transfusion; 2. Patients had allergies, immunodeficiency, and immunosuppression treatment; 3. Patients needed blood transfusion for acute blood loss such as trauma;

	
4. Female patients had positive result of pregnancy test;
 
5. Patients had conscious dysfunction and severe mental illness;
 
6. Patients were judged unsuitable for the study by the investigator.

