Intervention method	When the transfusion departments of the participating hospitals encounter the patients with the rare primary RhD negative blood group who needed to apply for blood transfusion in non-emergency situations, the application form and blood samples of the patients were sent to the reference lab of Guangzhou Blood Center for "Asia type" DEL blood group typing. The patients identified as "Asia type" DEL blood group and meeting the inclusion criteria will be provided the compatible RhD+ blood with the same ABO type after cross-matching test by Guangzhou Blood Center. RhD+ blood transfusion for the patients with "Asia type" DEL blood group was performed in the cooperated hospitals in line with the Technical Specifications for Clinical Blood Transfusion .
Evaluation index for effectiveness	Hemoglobin concentration (Hb); Hematocrit (Hct) etc.
Evaluation index for safety	
1. Incidence of anti-D alloimmunization;
 
2. Incidence of adverse blood transfusion reactions;
 
3. Observation of vital signs: temperature, heart rate, breathing, blood pressure etc.;
 
4. Laboratory testing;
 
5. Incidence and severity of other adverse events.

Visiting time	
Phase I of Visiting: -7~ 0 days before transfusion;
 
Phase II of Visiting: Blood transfusion treatment period (0~1 days) ;
 
Phase III of Visiting: 1 day to 1 month after blood transfusion;
 
Phase IV of Visiting: 1 month to 12 months after blood transfusion (based on the actual return visit in the hospital or follow-up at home) ;
 
Phase V of Visiting: Over 12 months after blood transfusion.

Statistical Analysis	As the "Asia type" DEL is a rare blood group with a frequency of around 0.75-1‰ in East and Southeast Asian population, it is not feasible to collect the enough samples to conduct the common statistical analysis. So, the descriptive statistics was regarded as the principal analysis method in this study. Continuous variables are described by number of cases, mean, standard deviation, median, minimum, and maximum; categorical variables are summarized by frequency and percentage. Statistical analysis is conducted using SAS9.4 statistical software.
Number of research centers	A total of 9 hospitals participate the trial.
Progress of the trial	The trial is expected to be completed within 48 months after beginning.

Protocol · Text

I. Research Background

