In recent years, more and more experimental and clinical data show that the most common "Asia type" DEL in Asian populations has the characteristics of "complete DEL". First, in several independent studies, the adsorption/elution experiments did not detect the absence of D antigen determinant in "Asia type" individuals [2, 14]. In addition, the synonymous mutation in exon 9 of the *RHD* gene (c.1227G>A, p.K409K) defined the "Asia type" DEL allele have been shown to cause abnormal mRNA splicing in molecular mechanisms studies. It resulted in a series of abnormal mRNA transcripts lacking exon 9, but further Mini Splicing function analysis in vitro found that the "Asia type" DEL allele express extremely low abundance transcripts including complete exon 9. This transcript may express a very low density of normal D antigen, thus forming the "Asia type" DEL phenotype [15]. Most importantly, several prospective and retrospective studies on observation of "Asia type" DEL pregnant women have shown that none of them developed alloanti-D. These studies involved the data from at least a thousand of "Asia type" DEL pregnant women (including more than 600 cases studied in our study and hundreds of samples included in several other studies) [6, 13, 16, 17] in China, which covering more than one million of people. In contrast, in the true D- Chinese population excluding "Asia type" DEL, the frequency of alloanti-D immunity ranges from 8.5% to 40% [13, 17]. Therefore, clinical data show that in the case of "Asia type" DEL Chinese pregnant women with high probability of having a normal RhD-positive fetus (>95%), alloanti-D will not be produced by D+ red blood cells from the fetus and newborn during pregnancy and childbirth.

Based on the results of previous research, it is extremely urgent to conduct a clinical trial of D+ blood transfusion in "Asia type" DEL patients, and to follow up in detail to obtain the anti-D immunization data in transfusion patients. This study is essential to set up a new blood transfusion strategy for "Asia type" DEL patient. In South Korea, two cases of "Asia type" DEL patients have been reported to receiving D+ blood transfusion, but still lacking of systematic clinical trial data to make the conclusion [18]. Therefore, the Korean National Blood Transfusion Guidelines (KNGBT) concludes that now there is not enough direct evidence to prove the safety of "Asia type" DEL

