2. During the blood transfusion, two medical staffs will bring the medical records to the patient's bed to check the patient's name, gender, age, blood type, medical record number, outpatient/ward room, bed number, etc., and confirm that the blood matches the cross-matching report. After checking the blood again, the blood transfusion begins using a transfusion device that meets the standards.
3. The blood should be transfused as soon as possible after taken back and not be stored. Before transfusion, to gently mix the ingredients in the blood bag and avoid violent shaking. No other drugs are permitted be added into the blood. If the dilution is needed, only saline for intravenous injection can be used.
4. Flushing the vessel with the intravenous saline before and after blood transfusion. When the patient receives continuous transfusion with the blood from different donors, after the previous bag of blood has been transfused, the transfusion set should be flushed with the intravenous saline, and then the next bag of blood could be continuously transfused.
5. During the process of blood transfusion, the speed of transfusion should be slow in the beginning and then faster, adjust the infusion rate according to the condition and age of the patient. It should be closely observed the recipients for adverse transfusion reactions. If abnormal conditions occur, the patient should be treated in time.

VI. Observation index

(I) Demographics

To collecting the ID information, date of birth, gender, and telephone number of the patient.

(II) Subject characteristics

The source of the patient, case number, chief complaint, current medical history, clinical diagnosis, blood type, pregnancy-labor history, history of infectious diseases, blood transfusion history,

allergy history, and family history.

(III) Safety observation indicators

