8. Including the supervision date, time, the name of the supervisor, the problems found during the supervision and handling methods, etc.

(V) The inspection of clinical research

The clinical trial supervision and management department and the sponsor could authorize the auditors to carry out systematic inspection on the clinical study to determine whether the implementation of the trial is consistent with the trial scheme and whether the reported data is consistent with the records of all clinical participating institutes, that is, whether the data reported or recorded in the case report form is the same with the medical record or other original records. The audit shall be performed by the person not directly involved in the clinical study.

XI. Data management

(I) Data entry and modification

The leading institute of the trial is responsible for the data entry and management. For the questions in the case report form, the data manager will send the questions to the researcher through the supervisor, and the researcher shall answer and return them as soon as possible. The data manager will modify, confirm and input the data according to the researcher's answers, and send the DRQ again if necessary.

(II) Data locking

After all doubts are solved and the established database is confirmed to be correct, the data manager should write the data management audit report and lock the audited data. The locked data file and statistical plan will not be changed.

XII. Statistical analysis

(I) The population for statistical analysis

The population for analysis includes safety analysis set (SS) and full analysis set (FAS).

1. The Safety analysis population: the subjects receiving at least one time of blood transfusion.
2. Full analysis population.

(II) Statistical analysis method

1. Demographic data and baseline analysis

* Analysis according to FAS;

- * Descriptive demographic data and other baseline characteristic values;
- * To calculate the number of cases, mean value, standard deviation, median, minimum and maximum for the continuous variables;
- * To calculate the frequency for the count and grade data.

2. Safety analysis

The SS population was used for safety analysis, and safety indexes included adverse events, laboratory examination, vital signs, etc. To summarize the data by stages and units. The adverse events will be aggregated.

* Adverse events

All adverse events will be coded with MedDRA.

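### Anti-D incidence is planned as one figure over all transfused patients, with no interval and no split by earlier D+ exposure, so 0/N cannot be read as 0/N first exposures

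*Combined protocol and SAP*

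**What the plan says.** The safety indices in the Protocol Abstract, and again in Sections VI (III) and VII (II), begin with "Incidence of anti-D alloimmunization", given as one quantity. Section XII (I) defines the safety set as everyone transfused at least once. Section XII (II) 2 breaks safety data down only by stage and unit and does not name anti-D. The Abstract makes the analysis descriptive, with frequency and percentage for categorical variables. No interval is specified anywhere.

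Inclusion criterion 2 reads "Male patients, or female patients ≥ 49 years of age, or female patients with severe illness and no further pregnancy plan", with no limit on parity. Section VI (II) lists "pregnancy-labor history, history of infectious diseases, blood transfusion history" among the subject characteristics. In Section XII these items can appear only under "Descriptive demographic data and other baseline characteristic values".

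Section I gives three relevant facts. Pregnant women with Asia-type DEL carry an RhD-positive fetus with more than 95% probability. Of at least a thousand such women studied, "none of them developed alloanti-D". DEL patients are normally typed as D- and given D- blood.

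**The concern.** The protocol's own background treats pregnancy and childbirth as contact with D+ red cells. The women it admits are 49 or older, or severely ill with no further pregnancy planned, so some will probably have been pregnant; the documents give no parity data. Men and never-pregnant women, who would usually have received D- units, are mostly meeting D+ cells for the first time.

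The two groups may not carry the same risk. Someone exposed earlier without making antibody may be a non-responder. Alternatively, earlier exposure may have primed a response that a new transfusion brings out. A single percentage cannot show which group the patients or the events come from. If no anti-D is seen, readers are likely to take the whole of N as evidence about a first D+ transfusion, although part of N cannot supply that evidence directly.

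**Working it through.** **The plan's own figure.** Section III cites 22.9% (53/231) anti-D in true D- recipients of D+ blood. 53/231 = 0.2294, so it reproduces (exact 95% interval 17.7% to 28.9%).

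**Inputs.** From the documents: one pooled incidence, no target sample size, no interval, probability of an RhD-positive fetus above 95%. Assumed, because the documents are silent: 40 patients screened for anti-D after transfusion, 25% to 50% of them previously exposed, no events.

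**Bound after zero events.** One-sided 95% upper bound = 1 − 0.05^(1/n). For the upper end of a two-sided exact 95% interval, replace 0.05 by 0.025.

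| Patients counted | n | One-sided | Two-sided upper end |
|---|---|---|---|
| All | 40 | 7.2% | 8.8% |
| First exposures, 25% exposed | 30 | 9.5% | 11.6% |
| First exposures, 50% exposed | 20 | 13.9% | 16.8% |

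**Other assumed sizes.** One-sided bound, pooled and then first exposures only:

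| N | Pooled | 20% exposed | 40% exposed | 60% exposed |
|---|---|---|---|---|
| 20 | 13.9% | 17.1% | 22.1% | 31.2% |
| 40 | 7.2% | 8.9% | 11.7% | 17.1% |
| 60 | 4.9% | 6.1% | 8.0% | 11.7% |
| 100 | 3.0% | 3.7% | 4.9% | 7.2% |

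**Direction.** Counting only first exposures gives the previously exposed no weight. To see what they could contribute, let r be the first-exposure risk and k·r the risk in the previously exposed, and solve (1 − r)^n1 × (1 − k·r)^n2 = 0.05. With N = 40 and 40% exposed, n1 = 24 and n2 = 16:

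| k | Upper bound for r | Pooled 7.2% is |
|---|---|---|
| 0 | 11.7% | too optimistic |
| 0.5 | 9.0% | too optimistic |
| 1 | 7.2% | correct |
| 2 | 5.1% | conservative |

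The documents do not fix k.

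**Against the 22.9% benchmark.** The smallest n with (1 − 0.229)^n at or below 0.05 is 12 (0.771^12 = 0.044); for 0.025 it is 15 (0.771^15 = 0.020). In the table of assumed sizes, the one-sided bound fails to exclude 22.9% only at N = 20 with 60% exposed. A two-sided interval also fails at N = 20 with 40% exposed, where its upper end is 26.5%.

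**The case against.** A reader might infer that pooling makes a zero result overstate the evidence. The documents do not support that direction. It holds only for k below 1. The argument for k below 1 is selection: antibody screening and cross-matching before transfusion (Section III and the flow chart) would tend to leave out women who had already made anti-D, so those enrolled would be non-responders. But Section I reports no anti-D in at least a thousand DEL pregnancies, which leaves few responders to screen out. Priming would push the other way. This objection stands, so the point has to be neutral on direction.

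It can also be said that the protocol never claims to estimate first-exposure risk. The aim in Section III is whether anti-D occurs in DEL patients after D+ transfusion, so as to decide how such patients should be treated. That policy covers women with and without past pregnancies, and the pooled incidence fits it. This stands too, and is why the pooled figure should remain the main one. Nor can one infer that only first-exposed patients supply new evidence: Section I notes that systematic transfusion data are lacking, so a transfused woman with past pregnancies is new evidence as well.

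The history separates the groups only roughly. Fetal D type, the D type of earlier units and earlier anti-D immunoglobulin are not listed items, although Section I mentions that immunoglobulin among the interventions given to DEL pregnant women. More than 95% is also the chance of an RhD-positive fetus, not a measure of how many fetal cells reached the mother.

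Finally, Section XII writes no anti-D analysis at all, so the pooling arises by omission. That is true, but the analysis still has to be written, and this distinction belongs in it.

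**Conclusion.** The point holds in a limited form. The plan would produce one anti-D percentage without an interval, over patients who differ in earlier D+ exposure, while collecting history that partly separates them. A result of 0/N must not be presented as 0/N first exposures.

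Under the assumptions of 40 patients and 25% to 50% previously exposed, counting first exposures alone moves the one-sided bound from 7.2% to between 9.5% and 13.9%. Those figures take nothing from the previously exposed; they do not show that the pooled bound is wrong. The pooled incidence remains a valid description of the mixed population that a transfusion policy would cover. The contrast with 22.9% survives in most of the assumed scenarios. What changes is how precise a first-exposure safety statement can claim to be.

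**What to change.** In Section XII (II) 2, state anti-D incidence explicitly as positive/screened with an exact 95% interval over all transfused patients who were screened, and keep it as the main figure. Report the number transfused but not screened.

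Add one descriptive table of the same quantity, with patients classified from history recorded before transfusion:

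- (a) no recorded pregnancy and no recorded D+ transfusion;
- (b) either of these.

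Flag patients whose earlier units have unknown D type, so that group (a) can be read with and without them. Base any statement about first exposure on group (a). Say in the text that the split is a proxy, because fetal D type and earlier anti-D immunoglobulin are not listed history items.

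Write this before data lock: Section XI (II) freezes the statistical plan with the data, and a split chosen after the results are known would carry less weight.

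The cost is a few lines of text and one table from history already listed for collection. Eligibility, treatment and visits do not change. The downside is small groups, wide intervals and some misclassification.

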patients receive D+ blood transfusion, and D+ blood transfusion is only allowed in the condition of emergency or lacking of D- blood supply for "Asia type" DEL patients [18]. In summary, this clinical study has important practical significance and can provide basic evidence whether anti-D alloimmunization will occur in "Asia type" DEL patients with ordinary D+ blood transfusion. If a new strategy of D+ blood transfusion in "Asia type" DEL patients can be established in the future, that is, the routine "Asia type" DEL testing in patients with a primary D- phenotype could be performed, and then to treat the "Asia type" DEL patients as ordinary D+ patients, rather than the rare D- patients in clinic. It will save at least 25% of rare D- blood in East and Southeast Asian countries, and it will also prevent "Asia type" DEL pregnant women receive anti-D immunoglobulin injection and other medical intervention/monitoring to prevent anti-D associated fetal neonatal hemolytic disease, which also could save the precious blood product anti-D immunoglobulin that derived from the sera from the D- volunteers who are sensitized.

II. Purpose of the trial

To explore the safety and effectiveness of RhD+ blood transfusion in Chinese "Asia type" DEL patients to lay the foundation for establishing a new blood transfusion strategy for "Asia type" DEL patients.

III. Design of the trial

The aim of this study is to analyze whether anti-D alloimmunization will occur in "Asia type" DEL patients after D+ blood transfusion, and then to compare the results with the data from the true D- patients received D+ blood transfusion to determine the "Asia type" DEL patients should be treated as D+ or D- patients in the future. The ideal study control group is the incidence of anti-D alloimmunization of true D- patients receiving D+ blood transfusion. But for ethical reasons (according to the requirements of *Technical Specifications for Clinical Blood Transfusion*, true D- patients can only be transfused with D+ blood in urgent situation or lacking of D- blood supply), and it is not appropriate to set up the control group (to transfuse D+ blood in true D- patients in non-emergency situations). Although the summarized rate of alloanti-D occurrence (22.9%, 53/231) [19-22] in true D- patients transfused with D+ blood in previous reported studies could be used as the control for the statistical analysis including sample size calculation, our study could not satisfy

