It is necessary to monitor and record the occurrence of the adverse events and its development in detail throughout the clinical trial.

(IV) Observation index of curative effects

To record the changes in hemoglobin concentration and hematocrit before and after blood transfusion.

(V) Concomitant treatment

During the study, all concomitant treatments or combined medications (from the beginning of the signed informed consent to the end of the trial) must be recorded in detail in the original medical record, including the intervention name, intervention purpose, dosage form, single dose, dosage unit, frequency of use, route of administration, start date, end date, and whether it is still being used.

For the combined treatment in the clinical research process, the corresponding analysis and recording should be done, especially the combined treatment in the event of adverse events, recorded and reported in a timely manner.

VII. Evaluation Index

(I) Main indicators for evaluation of the effectiveness

Hemoglobin concentration and hematocrit.

(II) The indicators for evaluation of the safety of the trial

1. Incidence of anti-D alloimmunization;
2. Transfusion r adverse reaction;
3. Vital signs: temperature, heart rate, breathing, blood pressure;

4. Blood routine (WBC, NEUT, Hb, Hct, PLT), renal function (Urea, Cr), liver function (ALT, AST, TBIL, DBIL, TP, ALB), electrolytes (K^+ , Na^+ , Ca^{2+} , P^{3+} , Mg^{2+}) before and after transfusion;
5. Incidence and severity of adverse events.

VIII. Steps of Clinical trial

(I) Phase I of Visiting: -7 ~ 0 days before transfusion

1. To explain the research purpose, methods, and requirements to the subjects, and to sign the informed consent for blood transfusion treatment by the two parties jointly;
2. To Collecting the demographics, characteristics, past/concomitant medical history of the subjects, and to conduct detailed physical examinations, and measure vital signs (including heart rate, breathing, blood pressure, body temperature; to measure blood pressure in a resting state);
3. Laboratory testing:
 - 1) "Asia type" DEL typing;
 - 2) Cross-matching test (only for the "Asia type" DEL patients);
 - 3) Blood routine: white blood cells (WBC), neutrophils (NEUT), hemoglobin (Hb), hematocrit (Hct), platelets (PLT);
 - 4) Four items for infections detection;

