 - 5) Liver function testing: alanine aminotransferase (ALT), aspartate aminotransferase (AST), total bilirubin (TBIL), direct bilirubin (DBIL), total plasma protein (TP), plasma albumin (ALB);
 - 6) Renal function testing: Urea, creatinine (Cr);
 - 7) Examination of coagulation function: prothrombin time (PT), activated partial thromboplastin time (APTT), thrombin time (TT), fibrinogen (FIB);
 - 8) Urine routine;
 - 9) Stool routine, occult blood test;
 - 10) Pregnancy test: The women patients who reach menopause, or are undergoing menstruation at the time of the test, or have undergone birth control surgery do not need to have a pregnancy test, but need to record the reason for not doing so.
 - 11) Electrocardiogram.
4. Combined treatment/medication;
5. Evaluation of the patients for participation of this study based on inclusion and exclusion

criteria.

(II) Phase II of Visiting: Blood transfusion treatment period (0~1 days)

1. To record the detail of transfusion, including the time of transfusion start and end, the type of transfusion, the volume of transfusion, and to observe the adverse reaction during the transfusion treatment;
2. Observation of vital signs: temperature, heart rate, breathing, blood pressure;
3. Observation and recording of adverse events;
4. Combined treatment/medication.

(III) Phase III of Visiting: 1 day to 1 month after blood transfusion

1. Physical examination, observation of vital signs (including heart rate, breathing, blood pressure, body temperature and to measure blood pressure in a resting state);
2. Laboratory testing:
 - 1) Detection of anti-D immune response (using antibody screening test);
 - 2) Blood routine: including white blood cells (WBC), neutrophils (NEUT), hemoglobin (Hb), hematocrit (Hct), platelets (PLT);
3. Observation and recording of adverse events;
4. Combined treatment/medication.

(IV) Phase IV of Visiting: 1 month to 12 months after blood transfusion

1. Laboratory testing:
 - 1) Detection of anti-D immune response (using antibody screening test);
 - 2) "Asia type" DEL blood group typing.
2. Observation and recording of adverse events.

(V) Phase V of Visiting: Over 12 months after blood transfusion

1. Laboratory testing:
 - 1) Anti-D immune response test (using antibody screening test);
 - 2) "Asia type" DEL blood group typing.
2. Observation and recording of adverse events.

IX. Adverse events, serious adverse events

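### Anti-D screens have wide windows with no target day, earliest informative day or maximum interval, and no rule says which screens make a patient anti-D negative

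*Combined protocol and SAP*

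**What the plan says.** Section III states the question: "The aim of this study is to analyze whether anti-D alloimmunization will occur in 'Asia type' DEL patients after D+ blood transfusion". Sections VI (III) and VII (II) put this endpoint first among the safety indicators ("1. Incidence of anti-D alloimmunization"), with no time point, minimum follow-up or case definition.

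Section VIII sets the follow-up. The headings are "III) Phase III of Visiting: 1 day to 1 month after blood transfusion", "IV) Phase IV of Visiting: 1 month to 12 months after blood transfusion" and "V) Phase V of Visiting: Over 12 months after blood transfusion". Each phase lists an antibody screen; in Phases III and IV the entry reads "Detection of anti-D immune response (using antibody screening test", and Phase V has an equivalent line. In Phase III the screen sits beside the blood routine. The flow chart in Section XV uses the same windows and adds a screen before transfusion. For Phase IV, the Protocol Abstract says timing is "based on the actual return visit in the hospital or follow-up at home".

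No section gives a target day, an earliest valid day, a number of draws or a maximum interval. Section XII (I) defines the safety set as everyone transfused at least once. Section IV (IV) classes patients with incomplete follow-up, or lost after transfusion, as dropouts, but does not say how they are handled for anti-D.

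**The concern.** A screen can show that anti-D has formed only if it is taken when the antibody would be present. The windows let the first screen fall one day after exposure and leave the second to the date of return or home follow-up. Without an evaluability rule, a negative on day 1 and a negative a year later can carry the same weight in the incidence.

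Two things are at stake. First, a patient whose only screen was very early adds to the denominator but could hardly have added to the numerator. Second, any missed antibody moves the result in one direction, towards zero, which is the favourable answer. The analysis is descriptive and has no fixed sample size, and Section III wants the result set against a rate of 22.9% in true D- recipients to decide how these patients should be treated in future. With few patients, zero or one case will shape that conclusion.

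**Working it through.** **Benchmark.** Section III gives 53/231. 53/231 = 22.94%, which reproduces the stated 22.9%. No sample size or power figure in the plan depends on the screening windows.

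**Longest permitted gap.** Take one draw per phase as the least that complies (the text lists the test per phase and gives no number of draws), and one month as 365.25/12 = 30.44 days.
- Screens on day 1, at month 12 (about day 365) and on day 366 meet all three windows. The gap after the first is 365 − 1 = 364 days, and the last two screens are one day apart.
- Screens on day 30, on day 31 and just after month 12 also comply. The gap is about 11 × 30.44 = 335 days.
- Phases III and IV share the month-1 end point, so a sample at month 1 fits either. Phase V has no per-patient upper limit; only the expected 48-month trial duration bounds it.

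**Whether another passage closes the gap.** The retest rule in Section VI (III) starts from an abnormal finding, so it does nothing for a patient who screens negative. The safety set asks only for one transfusion. The dropout criteria label incomplete patients but do not remove them from the anti-D denominator.

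**Share of Phase III draws that are too early.** The documents give no time to detectability, so this is an assumption shown over a range. With draws spread evenly over days 1-30 and the antibody first detectable on day d, the share drawn before day d is (d − 1)/29.

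| Assumed d | Calculation | Uninformative draws |
|---|---|---|
| 7 | 6/29 | 21% |
| 14 | 13/29 | 45% |
| 21 | 20/29 | 69% |
| 28 | 27/29 | 93% |

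**Effect of lost detection (illustration only).** If a share e of responders is undetectable at every screen taken, observed rate = true rate × (1 − e). For a true rate equal to the benchmark, e = 10%, 25% or 50% gives 20.6%, 17.2% or 11.5%.

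With no positives among n patients, the one-sided 95% upper bound is 1 − 0.05^(1/n). For an assumed n = 30 this is 9.5%. If only a share s of responders would be detected, the bound on the true rate is that figure divided by s: 9.5%/0.75 = 12.7%, and 9.5%/0.50 = 19.0%. The last is not far below 22.9%. Neither e nor s can be estimated from the documents.

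**The case against.** The strongest reply is that the schedule does not stop after Phase III. A patient who completes the protocol is screened again in Phase IV and in Phase V, so an antibody that lasts is picked up at one of them. This stands. A reader might infer from the 364-day gap that fully followed patients can readily be false negatives. That would need anti-D that forms and becomes undetectable before both later screens, and the documents give neither onset nor persistence.

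A reader might also take 45%, 69% or 93% as the proportion of cases missed. The figures describe single Phase III draws under assumed timing and do not carry through to the incidence in patients who have later screens.

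Nor do the documents say that sites will draw early, or that Phase IV depends wholly on hospital visits: follow-up at home is also allowed. And no passage states that a patient with only a day-1 screen is counted as negative. The plan is silent, and the safety-set definition leaves that reading open.

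What the objection does not answer is the patient who never reaches the later screens. Section IV (IV) itself foresees incomplete follow-up and loss after transfusion. For such a patient no assumption about a fading antibody is needed.

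**Conclusion.** The point holds in a limited form. It is certain from the text that the screens have no target day, earliest informative day or maximum interval, that a day-1 screen followed by one about 364 days later complies, and that no rule defines an anti-D negative patient. It follows that patients lost or dead after only an early screen can sit in the denominator without information, which lowers the observed incidence.

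The size of the bias cannot be computed from the documents. It depends on how many patients have only early screens and on the earliest detectable day. The 21% to 93% range rests on assumed days 7 to 28 and an even spread of draws. For patients who complete all phases, the expected consequence is late detection; a missed case is possible but unquantified. This should be corrected, because the endpoint is central and the change is cheap.

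**What to change.** Keep the number of screens and change their timing and their use.

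1. Give each screen a target time with a tolerance, in windows that do not overlap. Place the Phase III anti-D screen late in its window, separate from any early blood routine. Fix a Phase IV target and set an upper limit for Phase V.
2. Check the longest gap that the new windows permit (latest date of one screen minus earliest date of the one before) and make it clearly shorter than 364 days. For instance, a Phase IV screen allowed from month 3 with a Phase V screen allowed to month 15 would still leave 12 months.
3. State and justify an earliest informative day. Count any positive screen after transfusion, whenever drawn, checked against the pre-transfusion screen. A negative screen before that day should not, on its own, make a patient evaluable as anti-D negative. The flow chart marks the pre-transfusion screen, but the Phase I laboratory list in Section VIII omits it and should be aligned.
4. Report anti-D incidence among evaluable patients beside the full safety set, with the day of each patient's last screen. If follow-up is already complete, this step is still possible.

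The cost is protocol wording, visit reminders and a return visit for some discharged patients; no tests are added. Patients with only early negative screens leave the evaluable denominator. In so rare a blood group that loss may not be small, which is why both denominators should be shown.
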